2.1 Rationale for conducting the study

As well as the challenges described above, treatment compliance (persistence and adherence) represents a significant factor affecting the success of treatment (11).

Persistence is defined as the time between initiation and termination of therapy (12). Adherence describes whether patients take their medicine as prescribed. It comprises the initiation, implementation and termination of therapy (13). This compliance can be determined on the basis of the Morisky questionnaire. This consists of questions relating to intake behaviour (14). The questionnaire and its further developed version have already been used for assessing adherence during warfarin therapy, where it exhibited good validity (15, 16).

There are a variety of reasons for poor treatment compliance. These include patient-related aspects (e.g. socioeconomic status, personal convictions), but also disease-related (e.g. symptom severity) and medication-related (e.g. frequency of intake, side effects) aspects (17). This also applies particularly to patients with AF who require permanent oral anticoagulation (18). In terms of anticoagulation for the prevention of strokes, one important aspect is the fact that in the patients' subjective view it does not improve their condition and only the absence of a negative event (e.g. stroke) motivates them to continue treatment. This could limit treatment compliance and reduce the acceptance of side effects.

In addition, it has not yet been elucidated whether omission of the routine monitoring of coagulation status during treatment with dabigatran etexilate and the associated feedback to patients has any effect on treatment adherence in everyday therapeutic use. An analysis of Canadian health insurance data shows that drug persistence following the initiation of everyday care is higher during treatment with dabigatran etexilate than during VKA therapy (19).

No studies have yet been undertaken as to whether there are differences in persistence and adherence within the German care context between patients treated with Pradaxa® or VKA. For this reason, a contribution to the resolution of this question constitutes a relevant gain in knowledge.

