is performed according to Morisky. For patients who have not answered one or more questions, this score is not calculated. If the proportion of patients with missing answers is high (e.g. >20%), a sensitivity analysis will be performed, in which the score will also be

calculated if up to 2 questions per patient are missing²³. Patients who at the time of the visit are no longer on the initial therapy and those who have already discontinued the study before this time will be described separately from those for whom the Morisky score cannot be calculated for other reasons. Patients with missing values are analysed in terms of their baseline characteristics in comparison with patients with an evaluable Morisky score; patients with missing values will be stratified into the above-mentioned groups of study drop-outs, treatment drop-outs and patients with missing values for other reasons and the analysis will only be performed for strata with at least 200 patients (total and per treatment group).

The number and proportion of patients who fall into the different adherence classes will be presented for the dabigatran and VKA patients.

Coding

The current version of the Medical Dictionary for Drug Regulatory Activities will be used for coding adverse events. Concomitant medication will be coded using the current version of the WHO-DD.

Analysis of safety endpoints

For the analysis of adverse events, all patients documented in the CRF with at least one prescription for dabigatran etexilate or VKA will be included. Analyses of adverse events are descriptive and will be performed in accordance with Boehringer Ingelheim standards. In the analysis of adverse events, the focus is on treatment-emergent events. Events that occur in the period between the start of treatment and the permanent discontinuation of treatment or the end of the study (in patients in whom no permanent discontinuation of the medication is documented in the course of the study) + 6 days are categorised as treatment emergent and will be presented in frequency tables for dabigatran and VKA patients.

Adverse events that occur before or after this period will be assigned to “screening” or “post-treatment” and only presented in listings.

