Reasons for change 2:

After 6 months of site and patient recruitment it became evident that the targeted patient and site numbers will not be met and that recruitment time should be longer.

Therefore the planned patient number will be reduced to 1600 and site number to 800.

Recruitment time will be prolonged to 16 months (LPI December 2015), thus study duration will also increase. LPO is now planned for December 2016.

Other timelines will change accordingly.

CHANGE 3: ADAPT TIME SCHEDULE, SITE NUMBERS AND PATIENT NUMBERS

Section of the protocol: Statistics Section Determination of number of patients

It is planned to include a total of 4000 patients in this non-interventional, controlled, observational study (dabigatran etexilate: 2000 patients, VKA: 2000 patients).

Calculation of statistical power:

All analyses are purely exploratory by virtue of the non-interventional study design. On the following assumptions:

- 15% drop-outs /missing values after one year,
- 2000 dabigatran etexilate patients, 2000 VKA patients, with 66% of VKA patients with a matching partner in the dabigatran etexilate group (i.e. total number of patients in the 1:1 matched analysis is 2640)
- a persistence rate of 63% in the dabigatran etexilate group (cf. 1-year persistence with a 60-day permissible medication gap as reported by Zalesak ¹⁹)).

the power for a descriptive p value ≤ 0.05 in a 2-tailed test for the same persistence rates is as follows (dependent on the VKA persistence rate):

Assumed VKA persistence rate*	51%	53.8%	56.5%
Power	100%	99.7%	91.7%

* The calculations were performed with ADDPLAN6 and are based on survival time analysis test statistics and the endpoint variables "Time to permanent treatment discontinuation".

Was changed to:

It is planned to include a total of 1600 patients in this non-interventional, controlled, observational study (dabigatran etexilate: 800 patients, VKA: 800 patients).

Calculation of statistical power:

All analyses are purely exploratory by virtue of the non-interventional study design. On the following assumptions:

- 15% drop-outs /missing values after one year,
- 800 dabigatran etexilate patients, 800 VKA patients, with 66% of VKA patients with a matching partner in the dabigatran etexilate group (i.e. total number of patients in the 1:1 matched analysis is 1056)
- a persistence rate of 63% in the dabigatran etexilate group (cf. 1-year persistence with a 60-day permissible medication gap as reported by Zalesak (¹⁹)).

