the power for a descriptive p value ≤ 0.05 in a 2-tailed test for the same persistence rates is as follows (dependent on the VKA persistence rate):

Assumed VKA persistence rate*	51%	53.8%	56.5%
Power	97.8%	84.8%	61.1%

* The calculations were performed with ADDPLAN6 and are based on survival time analysis test statistics and the endpoint variables "Time to permanent treatment discontinuation".

Reasons for change 3:

After 6 months of site and patient recruitment it became evident that the targeted patient and site numbers will not be met and that recruitment time should be longer.

Therefore the planned patient number will be reduced to 1600 and site number to 800.

Observational Plan

Non-interventional study

Local Amendment

Local Amendment Number:	Local Amendment 2			
Country	Germany			
Date:	04. JAN 2016	 To be implemented only after documented approval of the IRB / IEC / Competent Authorities		
EudraCT No.:	n.a.	 To be implemented immediately in order to eliminate hazard – IRB / IEC / Competent Authority to be notified of change with request for approval		
BI Trial No.:	1160.218			
Investigational Product(s):	Pradaxa®	 Can be implemented without IRB / IEC / Competent Authority approval as changes involve logistical or administrative aspects only		
Title:	Drug persistence/adherence in patients being treated with Pradaxa® (dabigatran etexilate) or vitamin K antagonists (VKA) for stroke prevention in non-valvular atrial fibrillation (AF)			
Rationale for Local Amendment:	
After 15 months of patient recruitment 1050 / 1600 patients have been included until December 2015. For a meaningful data analysis and interpretation, the targeted patient number of 1600 patients should be met.
 
Therefore, recruitment time will be prolonged for one more year to 27 months (LPI December 2016), thus study duration will also increase. LPO is now planned for December 2017.
 
Other timelines will change accordingly.
 
In case 1600 patients will be included earlier, recruitment may be stopped before December 2016.
 
As this amendment is administrative and does not change the content or the nature of this non-interventional study, for readability reasons we refrain from changing every sentence in which site numbers, patient numbers or timelines are mentioned, except for the front page, study synopsis and statistics section.
			
Page 1 of 3				

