5.2 SECONDARY ENDPOINT(S)

- Proportion of patients with low, medium or high adherence at 6-months visit stratified for dabigatran etexilate and VKA. Categorisation of patients into low, medium or high adherence is done according to Morisky
- Reasons for permanent discontinuation of therapy

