7.5 SECONDARY ENDPOINT(S)

Absolute number and percentage of patients, who discontinue the initial treatment during study, will be summarized collectively and according to reasons for discontinuation for the dabigatran etexilate and VKA cohort, respectively.

The analysis of secondary endpoints will be based on the patient cohort resulting from the 1:1 matching.

The Morisky questionnaire consists of 8 question and will be answered at the 6- months visit. Each question can be scored with 0 or 1. For questions 1-7, 'no' will be scored with 0 and 'yes' with 1. For question 8, 'None/rarely' will be scored with 0 and all other answers with 1. The Morisky score is given by the sum of the values of each question, which implies a score between 0 and 8.

The categorisation of patients into low adherence (score >2), medium adherence (score=1,2) and high adherence (score=0) is done according to Morisky. The score will only be calculated for patients who answered all eight questions. In case that the proportion of the patients who did not answers all questions is too high (i.e. >20%) a sensitivity analysis will be conducted in which the score will be calculated if up to 2 questions per patient are missing. Patients who changed their initial treatment or withdrew from the study before the 6-months visit, will be displayed seperately from those for which the Morisky score could not be calculated for other reasons. Patients with missing data will be analyzed regarding to their baseline characteristics in comparision to the patients with an evaluable Morisky score; patients with missing values at the 6-months visit will be stratified into (i) the groups of study drop-outs, (ii) treatment drop-outs and (iii) patients with missing values because of other reason. The last mentioned analyses will only be done for strata of at least 200 patient (overall and for each treatment group).

Number and percentage of patients within the different adherence classes will be displayed for dabigatran etexilate and VKA patients, respectively. Furthermore the following subgroups will be presented for adherence (overall and for each treatment group):

- CHA₂DS₂-VASc-Score (<2, ≥2)
- Age (<65, 65- <75, ≥75)
- Previous stroke Yes, No)
- Medical specialty of attending physician (Internist, Cardiologist, General practitioner, Other)
- Daily dose of Pradaxa® at initial visit (2x110mg daily, 2x150mg daily) [Patients treated with Pradaxa® only]
- HAS-BLED-Score (<3, ≥3).

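### The 6-month adherence classes in effect cover only patients still on their first drug, the denominator is not stated, and the planned check on unscored patients is too coarse for the reduced sample

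*SAP*

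**What the plan says.** The endpoint in SAP 5.2 is "Proportion of patients with low, medium or high adherence at 6-months visit stratified for dabigatran etexilate and VKA". Protocol 5.1.1 defines it the same way. Neither restricts it to patients still on treatment.

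The flowcharts in both documents place the Morisky questionnaire at visit 3 only. For patients who have left the initial drug or the study by then, SAP 7.5 states: "Patients who changed their initial treatment or withdrew from the study before the 6-months visit, will be displayed seperately". The sentence goes on to contrast them with patients whose score is unavailable for other causes, so the separation is among patients without a score. The protocol has the same rule in 7.3 ("Patients who at the time of the visit are no longer on the initial therapy"). Both documents then divide the missing values into study drop-outs, treatment drop-outs and others. They plan to compare the baseline characteristics of these groups with those of scored patients, but only for strata of at least 200, overall and per treatment group.

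SAP 7 gives categorical tables a category for missing data, and SAP 6.6 labels missing values as such without imputing them. Neither document says whether that category enters the denominator of the adherence percentages.

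On the concept, Protocol 2.1 says of adherence: "It comprises the initiation, implementation and termination of therapy". It then names the Morisky questionnaire as the way to determine it.

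**The concern.** Comparing adherence between the two drugs is a secondary objective (Protocol 2.2), and matching is meant to make that comparison valid (Protocol 7.3, SAP 7). A table limited to patients still on their first drug conditions on persistence. Persistence is a post-baseline outcome, it is the primary endpoint, and the plan itself expects it to differ by arm. Baseline matching does not protect a comparison made in a subset selected in this way.

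If patients who stop early are also the poorer takers, the arm that loses more of them looks more adherent among those who remain. The adherence result could then point against the persistence result through selection alone, and a reader could not tell from the table which denominator was used.

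**Working it through.** **Inputs (Protocol, Local Amendment 1, Change 3, unless noted)**
- Dabigatran, 12 months: "a persistence rate of 63% in the dabigatran etexilate group".
- VKA, 12 months: "Assumed VKA persistence rate* 51% 53.8% 56.5" (percent).
- Size: "800 dabigatran etexilate patients, 800 VKA patients, with 66% of VKA patients with a matching partner in the dabigatran etexilate group", so 0.66 × 800 = 528 per arm, 1056 in all.
- Drop-out: 15% at one year.
- Stratum threshold: 200 (SAP 7.5).
- Assumed here, not in the documents: constant hazard of stopping; 50% high adherers among all starters in each arm; the adherence of stoppers, varied below.

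**1. The plan's own figures.** No rate, power or sample size is given for adherence. For persistence, the Schoenfeld formula with 528 per arm, exponential times and 15% drop-out gives power of 97.2%, 84.4% and 55.7%, against the stated 97.8%, 84.8% and 61.1%. The first two agree within a point. The third does not and should be rechecked separately. Nothing below depends on it, because only the persistence rates are used.

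**2. Share stopped by month 6** = 1 − √S(12).

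| Arm | S(12) | On drug at 6 months | Stopped | Stoppers per 528 |
|---|---|---|---|---|
| Dabigatran | 63% | 79.4% | 20.6% | 109 |
| VKA | 56.5% | 75.2% | 24.8% | 131 |
| VKA | 53.8% | 73.3% | 26.7% | 141 |
| VKA | 51% | 71.4% | 28.6% | 151 |

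The gap between arms is 4.2 to 8.0 points. If stopping is front-loaded (Weibull, shape 0.5), the shares are 27.9% against 33.2% to 37.9%.

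**3. Size of the possible artefact.** Suppose 50% of starters in each arm are high adherers and no stopper is one. High adherence among patients on drug is then 0.50 / (share on drug):
- dabigatran 0.50 / 0.794 = 63.0%;
- VKA 0.50 / 0.752 = 66.5% to 0.50 / 0.714 = 70.0%.

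The true difference is zero, but the table shows 3.5 to 7.0 points in favour of VKA (5.5 to 11.2 if stopping is front-loaded). At VKA persistence of 51%, if stoppers are half as likely as all starters to be high adherers (25%), the figures are (0.50 − 0.206 × 0.25) / 0.794 = 56.5% and (0.50 − 0.286 × 0.25) / 0.714 = 60.0%, a gap of 3.5 points. If stoppers do not differ, the gap is 0. If stoppers stay in the denominator, the extreme case shows 50% against 50%.

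**4. The 200-patient threshold.** It requires 200 / 528 = 37.9% of an arm. Expected stoppers are 109 and 131 to 151 per arm (105 and 126 to 145 after allowing for drop-out). In total, 109 + 131 = 240 to 109 + 151 = 260 pass the overall limit, but neither arm passes. Only VKA at 51% persistence with front-loaded stopping comes near (192 to 200). Study drop-outs by month 6 number about 528 × (1 − √0.85) = 41 per arm.

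Under the 4000-patient plan, with 2640 / 2 = 1320 matched per arm, the same shares give about 272 and 328 to 377 stoppers, so both arms would have passed. Local Amendment 1 says the reduced numbers will be the basis for the SAP. The SAP was finalised after it, in August 2015, and still uses 200.

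**The case against.** The strongest reply is that the plan is more open than a quick reading suggests.

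- **A reader might infer that stoppers vanish from the report.** They do not. They are displayed separately, discontinuations are reported by arm and reason (SAP 7.5), and Kaplan-Meier persistence at 6 months is given by arm in the same matched cohort (SAP 7.4).
- **The missing category in SAP 7 may keep them in the denominator**, and the artefact in the extreme example would then be zero. This stands as a possibility, but the plan should not leave it open. Nor does any sentence say outright that only patients on the first drug are scored; that follows from treatment drop-outs being a stratum of missing values.
- **A reader might infer that the analysis contradicts Protocol 2.1**, since adherence there includes termination. The documents do not support that. Protocol 2.1 assigns the measurement to the Morisky questionnaire, SAP 7.5 follows Protocol 7.3, and termination is captured by the primary endpoint. Concept and measure differ in scope, no more.
- **The bias is conditional.** Nothing in the documents shows that stoppers take their drug less well. The reasons that Protocol 6.1 lists for stopping are adverse events, intolerance and lack of efficacy.
- **Broken pairs alone do not unbalance a descriptive table.** Only selective loss does, and no paired adherence analysis is planned.
- **An all-patient percentage mixes persistence into adherence.** With an identical 50% high adherence among patients on drug, and 51% VKA persistence, it would read 39.7% against 35.7%. This is a fair reason to show both tables and not to make the combined measure the main comparison.

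The analyses are descriptive and no adherence test is planned. That lowers the stakes but does not remove selection from a side-by-side table.

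**Conclusion.** The point holds as a gap in specification with a plausible, conditional bias. The classes in effect describe patients still on the first drug, while the endpoint is worded for all patients and the denominator is missing. Projected loss by month 6 is 20.6% against 24.8% to 28.6%. This rests on the plan's assumed 12-month rates and a constant hazard, since no 6-month rate is given.

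The distortion ranges from zero to 3.5 to 7.0 points in the extreme case, and is larger if stopping is front-loaded. It needs two conditions: stoppers are poorer takers, and unscored patients are left out of the denominator. The documents settle neither, so it would be wrong to conclude that the adherence result will be biased.

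The firmest part is the threshold: by arm, the check meant to reveal selection would probably not be carried out at the reduced sample size. This is worth correcting but does not threaten the primary analysis.

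**What to change.** In SAP 5.2 and 7.5:
- State the denominator. Tabulate adherence over all matched patients in the classes high, medium, low, stopped initial drug before visit 3, and left study or no score.
- Keep the on-treatment table, labelled as conditional on persistence.
- Give the proportion on the initial drug with high adherence as a supplementary summary only.
- Lower or remove the 200-patient threshold, so that unscored patients are compared with scored patients by arm at the reduced sample size.

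The cost is SAP wording and one or two extra tables, with no new data. High-adherence percentages will be lower in the all-patient table than in the on-treatment table, and the text should say why.

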7.5 Determination of number of patients

It is planned to include a total of 4000 patients in this non-interventional, controlled, observational study (dabigatran etexilate: 2000 patients, VKA: 2000 patients).

Calculation of statistical power:

All analyses are purely exploratory by virtue of the non-interventional study design. On the following assumptions:

- 15% drop-outs /missing values after one year,
- 2000 dabigatran etexilate patients, 2000 VKA patients, with 66% of VKA patients with a matching partner in the dabigatran etexilate group (i.e. total number of patients in the 1:1 matched analysis is **2640**)
- a persistence rate of 63% in the dabigatran etexilate group (cf. 1-year persistence with a 60-day permissible medication gap as reported by Zalesak⁽¹⁹⁾).

the power for a descriptive p value ≤ 0.05 in a 2-tailed test for the same persistence rates is as follows (dependent on the VKA persistence rate):

Assumed VKA persistence rate*	51%	53.8%	56.5%
Power	100%	99.7%	91.7%

* The calculations were performed with ADDPLAN6 and are based on survival time analysis test statistics and the endpoint variables "Time to permanent treatment discontinuation".

8 Declaration of consent, data protection, NIS documentation

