Rationale for Local Amendment:	
After 6 months of site and patient recruitment it became evident that the targeted patient and site numbers will not be met and that recruitment time should be longer.
 
Therefore the planned patient number will be reduced to 1600 and site number to 800.
 
Recruitment time will be prolonged to 16 months (LPI December 2015), thus study duration will also increase. LPO is now planned for December 2016.
 
Other timelines will change accordingly.
 
New site and patient numbers will be used as calculation basis in the statistical analysis plan.
 
As this amendment is administrative and does not change the content or the nature of this non-interventional study, for readability reasons we refrain from changing every sentence in which site numbers, patient numbers or timelines are mentioned, except for the front page, study synopsis and statistics section.
	
Page 1 of 5		

Proprietary confidential information. © 2015 Boehringer Ingelheim International GmbH or one or more of its affiliated companies. All rights reserved. This document may not - in full or in part - be passed on, reproduced, published or otherwise used without prior written permission.
		

SIGNATURE PAGE(S)

This amendment

- concerns administrative matters only so that the coordinating investigator's signature will not be obtained.
- concerns matters dealing with design elements of the study, in- / exclusion criteria, observations, or safety or efficacy related study elements so that the coordinating investigator's signature needs to be obtained.

Trial Clinical Monitor

May 06 2015
Date

Trial Statistician

Boehringer Ingelheim
Biometrics & Data
Management

Team Member Medicine

Boehringer Ingelheim
Corporate Medical Affairs

Local Clinical Monitor

May 06 2015
Date

Boehringer Ingelheim
Medical Affairs Germany

SIGNATURE PAGE(S)

This amendment

concerns administrative matters only so that the coordinating investigator's signature will not be obtained.

concerns matters dealing with design elements of the study, in- / exclusion criteria, observations, or safety or efficacy related study elements so that the coordinating investigator's signature needs to be obtained.

Trial Clinical Monitor

May 06 2015

Date

Trial Statistician

May 07 2015

Date

Boehringer Ingelheim
Biometrics & Data
Management

Team Member Medicine

Date

Boehringer Ingelheim
Corporate Medical Affairs

Local Clinical Monitor

May 06 2015

Date

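### The 200-patient floor for the missing-adherence comparison was kept after the matched cohort was cut by 60%, so the within-arm comparison for treatment drop-outs is now not expected to run

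*SAP*

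**What the plan says.** Protocol 7.3 (Adherence) sorts patients without a Morisky score into study drop-outs, treatment drop-outs and those missing for other reasons, compares their baseline characteristics with those of patients who have a score, and adds a size condition: "the analysis will only be performed for strata with at least 200 patients (total and per treatment group"). At that time the target in protocol 7.5 was: "It is planned to include a total of 4000 patients in this non-interventional, controlled, observational study".

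Local Amendment 1 (April 2015) replaced this with: "It is planned to include a total of 1600 patients in this non-interventional, controlled, observational study". Its assumptions are "800 dabigatran etexilate patients, 800 VKA patients, with 66% of VKA patients with a matching partner in the dabigatran etexilate group", so that the "total number of patients in the 1:1 matched analysis is 1056". Its rationale adds: "New site and patient numbers will be used as calculation basis in the statistical analysis plan".

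The SAP became final in August 2015. Section 4 records no changes to the planned analysis. Section 7.5 bases the secondary endpoints on the matched cohort, scores only patients who answered all eight questions at the 6-month visit (a sensitivity analysis tolerates up to two missing answers if incompleteness is high), and repeats the condition: "The last mentioned analyses will only be done for strata of at least 200 patient (overall and for each treatment group").

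**The concern.** A fixed minimum stratum size that was reachable in 1320 patients per arm may be out of reach in 528. Adherence is observed only in patients who are still in the study and on their initial drug at month 6, and under the plan's assumptions the share lost to treatment discontinuation differs by arm (about 20% on dabigatran, 24% to 28% on VKA; see the working). The dabigatran-VKA adherence comparison is therefore open to differential selection. The by-reason baseline comparison is where the plan would show whether those lost differ from those scored, and only its per-arm form can show whether that difference is the same in both arms.

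**Working it through.** **Inputs.** From protocol 7.5 and Local Amendment 1, change 3: 66% of VKA patients matched 1:1; 15% drop-outs or missing values at one year; 12-month persistence 63% on dabigatran and 51%, 53.8% or 56.5% on VKA. From SAP 7.5: floor of 200, matched cohort, assessment at 6 months.

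**Plan's own figures.** Matched total = 2 × 0.66 × patients per arm. Before: 2 × 0.66 × 2000 = 2640 (1320 per arm). After: 2 × 0.66 × 800 = 1056 (528 per arm). Both reproduce. The cut is 1 − 1600/4000 = 60%.

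**Assumption not in the documents.** Discontinuation and drop-out each have a constant hazard and compete. Let l = −ln(12-month persistence) and c = −ln(0.85) = 0.1625. By month 6, in an arm of n patients:

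- treatment drop-outs = n × l/(l+c) × [1 − exp(−(l+c) × 0.5)]
- study drop-outs = n × c/(l+c) × [1 − exp(−(l+c) × 0.5)]

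Example, dabigatran: l = −ln(0.63) = 0.4620; the bracket is 1 − exp(−0.3123) = 0.2682. Treatment drop-outs are 0.4620/0.6246 × 0.2682 = 19.8% of the arm; study drop-outs are 7.0%.

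| Arm (12-month persistence) | Treatment drop-outs, n = 1320 | Treatment drop-outs, n = 528 | Study drop-outs, n = 1320 | Study drop-outs, n = 528 |
|---|---|---|---|---|
| Dabigatran (63%) | 262 | 105 | 92 | 37 |
| VKA (56.5%) | 315 | 126 | 90 | 36 |
| VKA (53.8%) | 339 | 135 | 89 | 36 |
| VKA (51%) | 363 | 145 | 88 | 35 |
| Pooled, over the VKA scenarios | 577–625 | 231–250 | 180–182 | 72–73 |

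**Other time patterns.** Ignoring competition, or spreading events linearly over the year, the n = 528 treatment drop-outs span 98–109 on dabigatran, 115–151 on VKA and 213–260 pooled. Pooled study drop-outs span 72–82 after the cut and 180–206 before it; per arm before the cut they reach at most 103.

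**Dependence on timing.** For dabigatran there is none at this matched size: 37% × 528 = 195, so even a full year of discontinuations falls short of 200. For VKA the full-year totals are 43.5% × 528 = 230 to 49% × 528 = 259, so reaching 200 by month 6 would need 200/230 = 87% to 200/259 = 77% of the year's discontinuations in the first half.

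**Dependence on matching.** If all 800 per arm were matched, the constant-hazard counts would be 159 on dabigatran (still short) and 191–220 on VKA.

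**Missing for other reasons.** The documents give no rate. This stratum would need 200/528 = 38% of an arm.

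**The case against.** The strongest reply has five parts.

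1. *The floor may apply table by table.* With 231–250 treatment drop-outs pooled, the overall comparison for the largest drop-out stratum would then still run. This stands as one reading. If both conditions must hold, neither drop-out stratum is analysed. The wording supports either, so a reader who infers that the check is switched off altogether goes beyond the text.

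2. *An unstratified comparison may carry no floor.* SAP 7.5 first announces the comparison of patients with missing data against those with a score, then the stratification, then the floor for the analyses mentioned last. Reading the floor as limited to the by-stratum tables is natural, and it leaves an all-missing comparison in place.

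3. *Other baseline tables exist.* Protocol 7.3 contrasts patients who discontinue treatment with those who do not, and SAP 7.4 contrasts premature study discontinuation with none, both without a floor. It would therefore be wrong to call this the only check of any kind. Those tables cover the whole study, however, and do not separate patients by whether, or why, the 6-month score is missing.

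4. *The cut did not cause the loss for study drop-outs.* Correct: per arm they numbered about 88–103 before the amendment, and pooled they were borderline at 180–206.

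5. *The floor need not depend on sample size.* The documents do not derive the 200, and a minimum for readable strata is not a calculation from N. So a contradiction with the amendment's sentence on new numbers is not shown. The consequence of leaving the floor in place follows regardless, and neither document comments on it.

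**Conclusion.** The point holds in a limited form. Under the plan's rates, the within-arm comparison for treatment drop-outs has moved from expected to run (about 262 and 315–363 per arm) to expected not to run (about 105 and 126–145). Whether the pooled treatment drop-out comparison runs depends on an ambiguous sentence. Study drop-outs fail on both readings, but the cut is not the reason per arm. What is at risk is the only planned comparison by reason for missingness, and above all its per-arm form.

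This rests on the plan's persistence and drop-out rates, the 66% matching yield, and constant hazards, which are an added assumption. The dabigatran result does not need the last of these at 528 per arm. The 15% figure combines drop-outs with missing values, so pure study drop-outs may be fewer than shown. The endpoint is secondary and every analysis is descriptive: this is a change that should be made, without bearing on the primary analysis.

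**What to change.** Delete the 200-patient condition from SAP 7.5 and record the deletion in SAP section 4. State that the descriptive baseline comparison with scored patients is always reported for each of the three reasons for missingness, overall and per treatment group, with stratum sizes shown. This also removes the ambiguity about how the floor applies.

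Scaling the floor in proportion (200 × 1056/2640 = 80) is not enough. It would restore treatment drop-outs in both arms, but study drop-outs would still be excluded per arm (about 35–37) and would be short or borderline pooled (72–73, at most 82).

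The cost is a few more descriptive tables. Some will rest on small strata and should be read with that in mind; since nothing is tested, small numbers are a reason for caution, not for leaving the tables out.
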